The study is designed to minimize in-person contact between participants and study staff or other persons at the CRS. The informed consent process, screening, and randomization may be performed remotely, in compliance with institutional and regulatory requirements.

At study entry, all participants will have either a remote visit or an in-person study visit at a secure location of the CRS, such as an isolation room, a room with a separate

entrance, or while in their car in a parking lot/parking garage. Participants will be given study treatment, a study symptom and adherence diary (i.e., Study Diary), and contact numbers for the study staff. Participants will provide medical and medication histories, and contact information for themselves, including their home address, **a list of local hospitals where they are likely to seek medical services if needed**, and for persons who will know about their study participation, in case study staff cannot reach the participant. Further, participants will be provided contact information for research staff in the event they require hospitalization. Participants will then complete **the Pre-Treatment page** of the Study Diary prior to starting study treatment.

The participant's first symptom(s) associated with COVID-19 and when it/they occurred will be recorded. Participants will also be observed taking their first dose of study treatment if it is an in-person visit.

Participants will record their symptoms, temperature (if participant is able to provide), medication adherence, and major events such as hospital visits and hospitalization in the Study Diary daily on Days 0-20, **in the evening** ([section 6.3.10](#)). Study staff will contact participants per the Schedule of Evaluations ([SOE](#)) to review study diaries. If participants cannot be reached after two attempts 24 hours apart, then their alternative contact person(s) will be called.

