4.0 SELECTION AND ENROLLMENT OF PARTICIPANTS

4.1 Inclusion Criteria

- 4.1.1 Participant (or legally authorized representative) provides informed consent prior to initiation of any study procedures.
- 4.1.2 Individual ≥18 years of age.
- 4.1.3 Documentation of confirmed active SARS-CoV-2 infection, as determined by a molecular test conducted at any US clinic or laboratory that has a Clinical Laboratory Improvement Amendments (CLIA) certification or its equivalent from any respiratory specimen collected <96 hours **from when the first dose of study treatment is expected to be taken.**
- 4.1.4 Experiencing at least one of the following SARS-CoV-2 infection symptoms **within 24 hours of screening:** fever (can be subjective) OR cough OR shortness of breath.
- 4.1.5 Agrees to not participate in another clinical trial for the treatment of COVID-19 or SARS-CoV-2 during the study period up until reaching hospitalization or 21 days, whichever is earliest.
- 4.1.6 Agrees to not obtain study medications outside of the A5395 study.

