6.3.10 Study Diary

Distribution of Study Diary

Participants will be provided a Study Diary at study entry. The Study Diary is posted on the DMC Portal in the Forms Management Utility.

Participants will be asked to keep a log of symptoms, temperature (if possible), medications they are taking, and major events such as urgent visit to an emergency room or clinic and hospitalization in their Study Diary on Days 0-20. At study entry, participants will complete the Study Diary prior to study treatment initiation. Depending on timing of each participant's dosing, some may complete HCQ/Placebo study treatment on Day 7 instead of Day 6 and need to report a Day 7 dose. Participants will be asked to complete the diary each evening.

Review of Study Diary

The Study Diary will be reviewed by study staff with each participant at the remote and in-person visits described in the [SOE](#) and the participant's answers recorded in the Participant Study Diary eCRF. If feasible, prior to or during the remote study visits, sites will request that the participant send images of each of their study diary entries to be reviewed at the next study contact.

Participants who report worsening illness from any cause during the trial may be referred to their health care provider or closest emergency room. Such instances will be recorded at the time of the notification, and during follow-up to assess study endpoints, i.e., hospitalization or death.

Review of Treatment Adherence

The treatment adherence portion of the Study Diary will be reviewed by study staff with each participant at the remote and in-person visits (if applicable), as described in the [SOE](#). The participant's answers of timing of doses taken will be recorded in the Adherence Assessment eCRF. If any doses are missed, the reason for the missed dose will be recorded.

Collection of Study Diary

The Study Diary will be collected per the [SOE](#). **If Day 20 is conducted remotely, arrangements should be made for future transfer of study diary from the participant to the study staff (i.e., mailing the study diary or sending images).**

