10.2.2 Secondary Outcome Measures

- 10.2.2.1 Death from any cause during the 21-day period from and including the day of the first (confirmed) dose of study treatment.
- 10.2.2.2 Death from any cause or hospitalization or urgent visit to an emergency room or clinic during the 21-day period from and including the day of the first (confirmed) dose of study treatment.
- 10.2.2.3 Death from any cause or hospitalization during the 24-week period from and including the day of the first (confirmed) dose of study treatment. Hospitalization is defined as requiring at least 24 hours of acute care in a hospital or similar acute care facility, including Emergency Rooms or temporary facilities instituted to address needs during the COVID-19 pandemic. Evaluation at a hospital or similar facility with less than 24 hours of acute care is not considered a hospitalization.
- 10.2.2.4 Premature discontinuation of study treatment due to an adverse event.
- 10.2.2.5 Occurrence of any cardiac adverse events from start of study treatment through Day 20.
- 10.2.2.6 Duration of fever defined as the last day in the participant's daily diary card on which a temperature greater than 100.4°F was recorded or a potentially antipyretic drug, such as acetaminophen or ibuprofen, was taken.
- 10.2.2.7 Duration of symptoms associated with COVID-19 disease defined as the last day in the participant's daily diary card on which a moderate or worse symptom was recorded. The set of targeted symptoms are the same ones that are used in many influenza studies, with the addition of the symptoms of loss of smell and loss of taste, which have been associated with COVID-19 infection. The symptoms from influenza studies are: cough, shortness of breath, feeling feverish, fatigue, muscle aches, diarrhea, vomiting, nausea, headache, sore throat, nasal obstruction (stuffy nose), and nasal discharge (runny nose). These symptoms are listed individually on the Study Diary that each participant will complete each day. The scoring is that used in influenza studies, whereby participants grade each symptom as absent (score 0), mild (1), moderate (2), or severe (3).
- 10.2.2.8 **Participant-specific area under the curve (AUC) of the symptom**

score associated with COVID-19 disease **over time (through Day 20)** defined as the sum of scores for the targeted symptoms (defined above) in the participant's daily diary record (each individual symptom is scored from 0 to 3).

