10.3 Randomization and Stratification

Eligible participants will be randomized using a 1:1 ratio to each of the study arms using permuted blocks with dynamic institutional balancing to minimize imbalances at any clinical site.

Randomization will be stratified by “high” vs “low” risk of severe disease, where “high” risk is defined by any of the following: age ≥ 60 years, or having any of the following conditions: hypertension, cardiovascular disease, diabetes, chronic kidney disease, chronic liver disease, chronic lung disease or moderate to severe asthma, severe obesity (BMI >40 based on self-report of height and weight), or immunocompromised due to disease or medication.

The study aims to enroll at least 50% of participants in the high-risk stratum. Initially, there will be no restriction on sites to enroll participants in the low-risk stratum. However,

after at least 200 participants have been enrolled, if fewer than 40% of enrolled participants are in the high-risk stratum, then sites may be asked to restrict enrollment to the low-risk stratum, such that, for every five participants they enroll in the low-risk stratum, at least five participants are enrolled to the high-risk stratum.

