10.6.2 Secondary Outcomes

The cumulative proportion of participants dying during the first 21 days of follow-up, and through to 24 weeks, and the cumulative proportion hospitalized/dying through to 24 weeks will be analyzed in a similar manner to the primary outcome.

Tolerability (occurrence of premature discontinuation of study treatment due to an adverse event) will be evaluated by estimating the proportion of participants who discontinue study treatment, and will be compared between arms using binary regression with adjustment for a participant's risk stratum. The proportion of participants who experience cardiac adverse events will be analyzed in a similar manner.

Duration of fever, duration of symptoms and duration of time to self-reported return to usual health will be summarized with descriptive statistics. Participant-specific durations of fever and symptoms will be compared between study arms using a two-sided stratified Wilcoxon test with a 5% Type I error rate. Total symptom score will be calculated on each day and the participant-specific area under the curve (AUC) over time will also be compared using a two-sided stratified Wilcoxon test. Participants who do not have complete diary cards due to hospitalization or death will be ranked in these analyses as having poorer outcomes than participants who survived without hospitalization.

The comparison of the proportion of participants with detectable SARS-CoV-2 RNA will use binary regression, with adjustment for risk stratum and pre-treatment SARS-CoV-2 RNA level. The model will be fitted using generalized estimating equations (GEE) to handle the repeated measurements, where the comparison between randomized arms will use a two-sided Wald test. Levels of SARS-CoV2 RNA levels will be compared between arms using non-parametric Wilcoxon rank-sum tests, separately at Day 6 and Day 20, considering results below assay limit as the lowest rank.

Descriptive summaries of clinical outcomes among those hospitalized will be provided by arm, recognizing that this would not be a randomized comparison, if restricted to participants who were hospitalized.

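### The planned tests of symptom-score AUC and symptom duration do not use the pre-treatment diary score, which costs some precision but not validity

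*Protocol*

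**What the plan says.** Section 10.6.2 names the tests. Participant-specific durations of fever and symptoms "will be compared between study arms using a two-sided stratified Wilcoxon test with a 5% Type I error rate", and for the total symptom score the "participant-specific area under the curve (AUC) over time will also be compared using a two-sided stratified Wilcoxon test". No pre-treatment symptom score is mentioned. Participants whose diaries are incomplete because of hospitalization or death are ranked worse than those who survived without hospitalization.

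The only stratification factor the protocol defines is in section 10.3: "Randomization will be stratified by “high” vs “low” risk of severe disease". It rests on age and listed comorbidities and contains no symptom information.

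A pre-treatment record is planned for everyone. Section 6.3.10 says "At study entry, participants will complete the Study Diary prior to study treatment initiation", and section 3.0 describes a Pre-Treatment page "of the Study Diary prior to starting study treatment". Section 10.2.2 lists 12 symptoms from influenza studies plus loss of smell and loss of taste, each scored 0 to 3, and adds: "These symptoms are listed individually on the Study Diary that each participant will complete each day".

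Entry criterion 4.1.4 sets a low floor: "Experiencing at least one of the following SARS-CoV-2 infection symptoms", namely "fever (can be subjective) OR cough OR shortness of breath". No minimum severity is required.

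**The concern.** AUC (10.2.2.8) accumulates the daily total score through Day 20, and duration (10.2.2.7) is the last day with a moderate or worse symptom. Both should depend on how ill the participant was at the start. With 14 items scored 0 to 3, the total can run up to 14 × 3 = 42, while eligibility can be met by a single mild symptom. The design therefore allows wide differences at entry, and the risk stratum does not measure them.

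The pre-treatment entry is made before treatment can act, so it is a legitimate covariate. Without it, variation that the baseline score could explain stays in the test. At stake is power for objective 1.3.3, the effect on severity and duration of symptoms, in outcomes collected from all 2000 participants. In the same section the comparison of detectable viral RNA is adjusted for its pre-treatment level, so the idea is already in the plan.

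**Working it through.** **Is there a figure to reproduce?** Not for these outcomes. The protocol gives no effect size, variance, correlation or power for AUC or duration. Its stated 90% power (section 10.4) belongs to the primary outcome. That figure reproduces: with 950 evaluable per arm (1000 less 5%) and 15% versus 10%, power is 91.0% at a single look, and 89.9% at a final nominal level of about 0.043 (an approximation for four O'Brien-Fleming looks). The present point does not affect it.

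**Inputs.** From the protocol: the tests, the worst-rank rule, two risk strata, 2000 participants, two-sided 5%. Assumed: the rank correlation rho between pre-treatment score and outcome.

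**The two statistics.** In stratum k let N_k be the number of participants, n_1k and n_0k the numbers on active and placebo, and W_k the rank sum of the active arm.

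- Planned (van Elteren form): T = Σ [W_k − n_1k(N_k + 1)/2] / (N_k + 1).
- Adjusted: T_adj = Σ {[W_k − n_1k(N_k + 1)/2] − b_k·D_k} / (N_k + 1). Here D_k is the active arm's baseline total minus n_1k times the stratum mean, and b_k is the slope of outcome rank on baseline within the stratum, arms pooled.

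The outcome ranks enter T_adj unchanged; the adjustment is one term per stratum. The variance of T_adj is about (1 − rho²) times that of T, and the equivalent gain in sample size is 1/(1 − rho²) − 1.

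| Assumed rho | Variance removed | Equivalent extra participants | Equivalent N for 2000 | 80% power becomes |
|---|---|---|---|---|
| 0.3 | 9% | 10% | 2198 | 83.6% |
| 0.4 | 16% | 19% | 2381 | 86.4% |
| 0.5 | 25% | 33% | 2667 | 89.9% |
| 0.6 | 36% | 56% | 3125 | 93.8% |

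**Does the gain survive worst-ranking?** Trials were simulated with 950 per arm, two risk strata, about 12.5% worst-ranked (the mean of 15% and 10%) equally in both arms, and 1500 runs per setting. Worst-ranking was more likely with a higher baseline score. The treatment shift was an assumed 0.15 SD. The adjusted test had the T_adj form, with baseline as within-stratum ranks.

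| Assumed rho | Rank correlation after worst-ranking | Power, planned test | Power, adjusted test |
|---|---|---|---|
| 0.3 | 0.29 | 68% | 72% |
| 0.5 | 0.44 | 67% | 77% |
| 0.7 | 0.59 | 67% | 84% |

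With no treatment effect (rho 0.2 to 0.7), rejection rates ran from 4.2% to 6.3%. The simulation standard error is √(0.05 × 0.95/1500) = 0.56 percentage points. The highest pair, 5.9% planned and 6.3% adjusted, came from the same simulated trials, and the two tests never differed by more than 0.4 points.

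A less favourable case: where hospitalization was simulated as unrelated to baseline score, again with 12.5% worst-ranked, rho of 0.5 fell to 0.37. The variance removed is then 0.37² = 14% instead of 25%, worth 1/(1 − 0.137) − 1 = 16% more participants instead of 33%.

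**The case against.** The strongest reply is that nothing here is wrong. Section 10.6 calls itself an outline and leaves detail to the statistical analysis plan, which may add an adjusted analysis. That is fair as to supportive analyses, but section 10.6.2 does name the test, so the choice can be reviewed as stated.

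The planned test is also valid, and this stands in full. A reader might infer that a chance difference in baseline severity would bias the result or inflate false positives. It would not: such imbalances are already counted in the 5% error rate.

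A reader might also infer that much of the between-person variation is left in the test. The documents do not support that. The share is rho squared, no rho is given, and it is 9% at the low end of the assumed range. The figures suit AUC best; duration, the last day with any moderate symptom, may relate differently to baseline.

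That the Pre-Treatment page holds all 14 scored items is inferred from sections 6.3.10 and 10.2.2, since the page is not shown. The RNA precedent is mixed too: RNA levels, unlike detectability, are compared by an unadjusted Wilcoxon test.

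Finally, one way of adjusting would damage the plan. Regressing outcome ranks on baseline and running a Wilcoxon test on the residuals re-orders participants, so someone who died or was hospitalized with a high baseline score can land better than a survivor never hospitalized. In a simulation at an assumed rho of 0.5, 64% to 95% of worst-ranked participants fell below at least one such survivor, and 1% to 8% of event-survivor pairs were inverted. This objection is correct against that method, but not against T_adj, which leaves the ranks alone.

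**Conclusion.** The point holds as a question of efficiency in two secondary outcomes. The named test ignores a pre-treatment measurement planned for everyone. The cost is about rho squared of the variance, or 9% to 36% for an assumed rho of 0.3 to 0.6, somewhat less where the worst-rank rule lowers the rank correlation. The size rests on that assumed range, on the pre-treatment page yielding a usable total score, and, for duration, on a correlation that may differ from the one for AUC. There is no bias, no inflation of type I error and no effect on the primary outcome. The change is worth making because it costs little and must be fixed before unblinding to be credible.

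**What to change.** First confirm that the Pre-Treatment diary page records the targeted symptoms on the 0 to 3 scale. Then amend section 10.6.2 for outcomes 10.2.2.7 and 10.2.2.8 along these lines:

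- Outcome ranks are assigned within risk stratum, with the worst-rank rule for hospitalization and death unchanged.
- Arms are compared by a stratified nonparametric rank analysis of covariance, that is, the van Elteren statistic with randomization-based covariance adjustment for the between-arm difference in pre-treatment total symptom score. Residuals are not re-ranked.
- A missing pre-treatment score is replaced by the stratum median.
- The unadjusted stratified Wilcoxon test is reported as supportive.

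The cost is a few sentences, slightly more analysis work, and a test that is less simple to report. No new data are needed.

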Once infection occurs, the clinical course is variable. Best current data suggest that fewer than 2.5% of infected persons will show symptoms within “2.2 days (CI, 1.8 to 2.9 days) of exposure, and symptom onset will occur within 11.5 days (CI, 8.2 to 15.6 days) for 97.5% of infected persons” [3]. In most (~80%) cases, COVID-19 presents as a mild-to-moderately severe, self-limited acute respiratory illness with fever, cough, and shortness of breath. It remains unclear exactly what the rate of progression of COVID-19 is and what the predictors are for complications, including pneumonia, acute respiratory

distress syndrome (ARDS), kidney failure, and death. It is clear that older age, male sex, and comorbidities including diabetes and hypertension increase the risk for worse outcomes (Figure 2.1-1) [4-6]. In a recent meta-analysis, the main clinical symptoms were fever (88.5%), cough (68.6%), myalgia or fatigue (35.8%), expectoration (28.2%), and dyspnea (21.9%). Minor symptoms included headache or dizziness (12.1%), diarrhea (4.8%), and nausea and vomiting (3.9%) [7]. Laboratory examinations showed that lymphocytopenia (64.5%), increase of C-reactive protein (CRP) (44.3%), increase of lactate dehydrogenase (LDH) (28.3%), and leukocytopenia (29.4%) were more common in those with COVID-19 [4, 8].

Shedding

Viral infections jump from host to host through a variety of pathways. CoVs do this through respiratory droplets. Understanding this shedding is important to understanding epidemic spread and how shedding relates to disease progression. Best evidence available now suggests that viral shedding, especially in upper respiratory secretions, is detectable around 2 days before symptoms develop and continues throughout the symptomatic phase. This shedding can be quite high during active disease and can continue for up to 37 days, with a quarter of persons still shedding at 3 weeks, as detected by nasopharyngeal swabs [4].

Biomarkers

The literature also points to a systemic inflammatory response that predicts disease progression and death. Having a biomarker panel that can predict such progression early would be helpful in making clinical decisions and triaging clinical care [4]. In particular, patients requiring ICU admission had higher blood levels of interleukin (IL)2,

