6.2.2 Entry Evaluations

Screening and entry visits may be combined. The study entry visit **can be** either a remote or in-person visit. **Participants must begin study treatment within 96 hours of the collection time of the respiratory specimen that was positive for SARS-CoV-2 and qualified them for the study.** The first dose of study treatment must be directly observed at the in-person visit or confirmed remotely (by video or telephone) **for those with remote study entry visit. The day of the first dose is considered Day 0.**

Depending on how the screening and study entry/Day 0 visits are conducted, randomization must occur after screening but may occur prior to the study entry/Day 0 visit, or at the study entry/Day 0 visit.

Those participants that agree to the additional sample collection must have the NP swab, self-collected nasal swab, and blood collected prior to receiving the first treatment dose.

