- 10.2.2.9 Time to self-reported return to usual (pre-COVID) health.
- 10.2.2.10 Level (detectable versus not detectable, and continuous) of SARS-CoV-2 RNA from self-collected nasal and site-collected NP swabs at entry and Days 6 and 20 among subset.

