11.4 Anticipated Outcomes

HCQ plasma levels will be associated with increased rate of viral clearance. Baseline viral load will also be an important determinant of viral clearance.

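### RNA level is compared by plain rank-sum tests that ignore the pre-treatment RNA level, although detectability on the same swabs is adjusted for it: valid, but avoidably imprecise

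*Protocol*

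**What the plan says.** Secondary outcome 10.2.2.10 has two halves measured on the same swabs: "Level (detectable versus not detectable, and continuous) of SARS-CoV-2 RNA", at entry, Day 6 and Day 20 in the subset.

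Section 10.6.2 analyses the halves differently:

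- **Detectability:** binary regression fitted by GEE, "with adjustment for risk stratum and pre-treatment SARS-CoV-2 RNA level".
- **Level:** RNA "levels will be compared between arms using non-parametric Wilcoxon rank-sum tests, separately at Day 6 and Day 20", with results below the assay limit placed at the lowest rank. Neither entry RNA nor risk stratum is mentioned.

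The preceding paragraph of 10.6.2 uses stratified Wilcoxon tests for fever and symptom duration, and says of the symptom-score AUC that it "will also be compared using a two-sided stratified Wilcoxon test". So the section writes stratification in where it is meant.

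On the covariate itself, section 6.2.2 says that subset participants "must have the NP swab, self-collected nasal swab, and blood collected prior to receiving the first treatment dose", and section 11.4 states: "Baseline viral load will also be an important determinant of viral clearance".

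**The concern.** Objective 1.3.2 asks about both the frequency of detection and the level of RNA, and the subset that answers it has only 200 participants. Entry RNA is a true pre-treatment covariate, is already collected, and is expected by the protocol itself to predict clearance. It is used for one half of the outcome and left out of the other, and no reason is given.

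An SAP that follows this sentence inherits the weaker method. At stake is the power of the comparison of RNA level, mainly at Day 6. Neither type I error nor the primary outcome is affected.

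**Working it through.** **Inputs from the protocol.** Subset of 200 who start treatment (Schema); 1:1 allocation (10.3), so about 100 per arm; values below the limit at the lowest rank (10.6.2). Section 2.1 describes viral shedding "with a quarter of persons still shedding at 3 weeks", which suggests about 75% of values below the limit near Day 20. The protocol gives no power, effect size, SD, entry-to-follow-up correlation or Day 6 share below the limit for this outcome. There is therefore no figure of its own to reproduce, and those quantities are assumed and varied below.

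**Step 1: approximation with no values below the limit.** Adjusting for a covariate with correlation ρ multiplies the variance by 1 − ρ². Take an effect that gives the rank-sum test 80% power. With relative efficiency 0.955, the effective n is 0.955 × 100 = 95.5 per arm, and the effect is (1.960 + 0.842) × √(2/95.5) = 0.405 SD. Adjusted power is Φ(2.802/√(1 − ρ²) − 1.960), and the equivalent unadjusted size is 100/(1 − ρ²) per arm.

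| ρ | 1 − ρ² | Adjusted power | Equivalent n per arm |
|---|---|---|---|
| 0.3 | 0.91 | 84% | 110 |
| 0.5 | 0.75 | 90% | 133 |
| 0.7 | 0.51 | 97% | 196 |

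**Step 2: simulation with values below the limit.** Set-up: 4,000 trials per setting; bivariate normal log RNA at entry and follow-up; two equal strata with 1:1 allocation within each; values below the limit tied at the lowest rank; two-sided 5%. The Monte Carlo standard error is about 0.7 points or less for power. The table compares the tie-corrected rank-sum test with stratified rank analysis of covariance (ANCOVA).

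| Setting (assumed) | Evaluable | Rank-sum | Adjusted, ρ = 0.3 / 0.5 / 0.7 |
|---|---|---|---|
| Day 6: 0.42 SD, 30% of placebo below limit | 200 | 77-79% | 80% / 87% / 95% |
| Day 6: same | 180 | 73-74% | 78% / 83% / 93% |
| Day 20: 0.5 SD, 75% of placebo below limit | 200 | 68-70% | 70% / 74% / 78% |
| Day 20: same | 180 | 64-65% | 65% / 69% / 75% |

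A repeat with separately written code agreed within about 2 points in every cell.

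**Step 3: checks on the comparison.**

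- *Validity.* With no effect, every test rejects in 4.4-5.4% of trials.
- *Useless covariate.* At ρ = 0, power is 78.7% for rank-sum v 78.2% adjusted at Day 6, and 68.3% v 68.0% at Day 20.
- *Entry values below the limit.* With 10% of entry values also below the limit, Day 6 power at ρ = 0.5 is 78.0% v 86.5%.
- *Source of the gain.* At ρ = 0.5, adding the stratum changes Day 6 power by 0.2 points if the strata differ by 0.2 SD, 1.5 points at 0.5 SD, and 7 points only at 1.0 SD. Nearly all the gain comes from entry RNA.

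**The case against.** The strongest reply is that nothing here is wrong. The rank-sum test is valid and standard, and it handles results below the limit sensibly. Two halves of an outcome may be analysed by different methods without contradiction. Section 10.6 calls itself an outline and defers detail to an SAP that is not shown, which could add an adjusted analysis. Objective 1.3.2 already has one baseline-adjusted comparison, for detectability, and the pharmacology plan models viral clearance separately.

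The size is also open to challenge, since it rests on assumptions:

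- At ρ = 0.3 the gain is only a few points.
- If the Day 6 effect were 0.6 SD, the rank-sum test would already have about 97% power, against 98-99% adjusted at ρ = 0.3 to 0.5.
- At Day 20, using the Day 6 effect of 0.42 SD with 75% below the limit, power rises only from about 54-56% to about 60% at ρ = 0.5.
- The shedding figure comes from a cohort that the reference list describes as adult inpatients, whereas this trial enrols outpatients. Section 2.1 also does not say from when the three weeks are counted.

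Most of this stands as a limit on size. It does not remove the point. Section 10.6.2 does not leave the method open: it names an unadjusted test for this outcome. No passage brings entry RNA into the between-arm comparison of levels. None of these replies identifies a material cost of adjusting, since even an uninformative covariate loses about 1 point of power or less.

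**Conclusion.** The point holds. Section 10.6.2 fixes a valid but less efficient test for RNA level and leaves unused a mandatory pre-treatment measurement that the protocol itself considers prognostic.

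The loss is about 1 to 3 points of power at Day 6 if ρ is 0.3, about 8 to 10 points at 0.5 and about 16 to 18 at 0.7, with 100 per arm and a 0.42 SD effect. At Day 20 it ranges from almost nothing to about 10 points. These sizes rest on assumed correlations, effects and shares below the limit, so confidence in the size is moderate, while the direction is secure. The missing stratification matters little by itself.

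The change should be made because it is nearly free. It concerns one half of one secondary outcome in the subset of 200 and has no bearing on the primary conclusion.

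**What to change.** In section 10.6.2, replace the rank-sum tests for RNA level with a rank analysis of covariance on the pre-treatment RNA level from the same swab type, stratified by risk group, done separately at Day 6 and Day 20. Keep results below the assay limit at the lowest rank. This uses the covariates already chosen for detectability and preserves the rank-based approach.

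The cost is one sentence, carried into the SAP before unblinding. No new data are needed, because the entry swabs are already required.
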